9.1 MAPPING COHORTS

In the first cohort of up to 15 patients, AF mapping (utilizing CMA) will be performed but will not be utilized to guide the ablation procedure. That is, ablation will be based on standard approaches only. The purpose of this initial cohort is to validate the software and mapping procedure. Brief operator learning curve relating to the mapping procedure is expected. Proper sampling is necessary in order to achieve full spatial coverage of an entire chamber. The benefit of the technology includes infinite spatial resolution with unlimited multiple synchronized sample locations throughout the atria, but that unlimited sampling must be balanced with time added to the procedure for sampling and software computation. The first cohort of patients is designed to allow for this learning curve to be normalized between the catheter operators and the software operators. Performing the mapping alone, Kurian T, et al. have seen no procedure related adverse events in over 61 patients. As such, it is safe and worthwhile to take an initial cohort of patients to normalize the mapping process in persistent AF patients where the chambers are often diseased, complex and dilated requiring operator skill to

sample an entire chamber appropriately. The consistent convergence of the CMA software within five minutes signifies that a balance has been struck between the amount of sampling data supplied to the software and the operator's satisfaction in adequate sampling of the patient's anatomy. Over the course of these cases, if the software algorithm is converging to a solution consistently within five minutes of processing time, the size of this validation cohort may be reduced to less than 15.

In the second cohort of patients (potentially patients 16-65), AF mapping (utilizing CMA) will be performed and used to point the operator to regions within a heart chamber that should be interrogated further for suspicious electrogram activity, as measured by the St. Jude Ensite System, and ablated if the suspicious electrogram activity persists.

➤ **Empiric ablation (CFAE or linear ablation) is not permitted**

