9 PATIENT ENROLLMENT AND WITHDRAWAL

Patients meeting the study inclusion criteria will be identified in the outpatient or inpatient setting by investigators. Patients will be followed by one of the study site principal or co-investigators.

The study will typically be described (including the risks and benefits) during the initial clinic or hospital visit. Consent will typically be obtained at the time of the initial assessment if it is clear that the patient truly understands the nature of the study. Alternatively, the patient will be encouraged to take a copy of the consent form home to contemplate whether he/she would like to be enrolled in the study. Only patients who voluntarily provide consent will be included in this study. Consent will be obtained prior to undergoing the ablation procedure. Patients will be able to withdraw from the study at any point without compromising their medical care. All data will be de-identified and protected in accordance with institutional and HIPAA guidelines, including 1) de-identification of all geographic subdivisions smaller than a state; 2) all elements of dates related to the individual; 3) telephone and fax numbers; 4) email addresses; 5) social security number, medical record, health plan beneficiary, account, and certificate/license numbers; 6) vehicle identifiers; 7) device identifiers; 8) URLs and IP addresses; 9) biometric identifiers; and 10) photographic images.

[figure not shown]
Eligible subjects will be consented for participation in the trial prior to undergoing AF ablation. Patients are considered enrolled once consented. Patients will be followed for 12 months. Patients who do not undergo an ablation procedure within 90 days of enrolling will be considered to be screen failures. Additionally, if a patient does not have any ablation performed that is a result of the mapping completed by the CMA software, the patient will be considered a screen failure. Patients who are deemed to be screen failures may be considered for re-enrollment should they require a later AF ablation procedure.

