- All drivers are to be sequentially ablated or isolated using the St Jude Ensite system to navigate ablation catheter to the anatomic region identified by the AF mapping as a potential driver domain, assessing the local electrograms via St. Jude Ensite system and delivering ablation via St. Jude ablation catheter. If rhythm is still not organized then ablation sites are visited again to ensure adequate ablation.
- Then, Re-assess rhythm
- If AF persists, Real time electrogram processing mapping should be repeated (**Map_{Re1,2,...}**) and additional driver regions targeted.
- If the rhythm organizes to an atrial tachycardia, it should be targeted for ablation
- If rhythm is still in AF despite elimination of all drivers based on repeated Maps or if no drivers are localized- the patient will be cardioverted to sinus rhythm (Number of remaps is at the discretion of operator)

- If during AF or AT ablation- the patient reverts to sinus rhythm- ablation is complete at that site as per operator definition of sufficient ablation. Additional drivers localized during mapping will also be targeted despite sinus rhythm
- Empiric ablation (CFAE or linear ablation) is not permitted

Presenting rhythm - Atrial fibrillation

- Electro anatomic maps of right and left atria are created and PV isolation is assessed with multielectrode mapping catheter.
- **Map_{spontAF}** will be acquired CMA software running on the laptop adjacent to the 3D Mapping System.
- Prior to ablation- LAA and RAA cycle length are to be measured over 10 beats.
- Ablation of drivers can be initiated in chamber with faster CL or with greater number of identified drivers
- Drivers can be addressed in order of importance as suggested by maps.
- Periodic reassessment of TCL in LAA and RAA to be done to help direct operator to chamber of interest- e.g. if there is significant gradient between RAA and LAA such that RAA is faster then drivers can be pursued in RAA prior to completion of all driver regions of LA
- All drivers are to be sequentially ablated or isolated using the St Jude Ensite system to navigate ablation catheter to the anatomic region identified by the AF mapping as a potential driver domain, assessing the local electrograms via St. Jude Ensite system and delivering ablation via St. Jude ablation catheter. If rhythm is still not organized then ablation sites are visited again to ensure adequate ablation.
- Then, re-assess rhythm

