10.4 POST-PROCEDURE

10.4.1 POST-PROCEDURE FOLLOW UP

- Discharge criteria decisions will be made at the discretion of the primary operator per current guidelines.
- Medication and adverse event review will be performed prior to discharge.
- Complications including vascular, stroke, heart failure, pericardial effusion, tamponade, bleeding, and death will be documented.
- The post ablation blanking period will last 3 months only - any AAD is permitted but should be stopped by 8 weeks after the study procedure
- The total number of episodes of post-blanking AT or AF episode > 30 seconds will be recorded

- Patients will undergo continuous 7 day ambulatory monitoring at 3, 6 and 12 months
- Review of medications and adverse events will be performed at the 3, 6 and 12 month follow up
- At any time during the follow-up period, patients will be allowed a second ablation procedure using the CMA software should recurrence of AF occur. Data from the second procedure will be recorded.

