13 STUDY MANAGEMENT

13.1 Study Data Collection and Processing

The Case Report Form (CRF) is an integral part of the study and subsequent reports. The CRF must be used to capture all study data recorded in the patient's medical record. The CRF must be kept current to reflect patient status during the course of the study. Patients will be identified by a 5-digit number and their initials. The investigator must keep a separate log of patient names and medical record numbers (or other personal identifiers) for their own reference. All study-related documents (CRFs, source medical records, regulatory binder) must be kept in a secure, locked environment with access limited to study personnel only.

The PI is responsible for ensuring the following: 1) adherence to the protocol; 2) verifying adherence to local regulations on the conduct of clinical research; and 3) ensuring completeness, accuracy, and consistency of the data entered in the CRF.

Final CRFs in human readable format must be reviewed and verified for accuracy by the study site Principal Investigator and signed-off. A copy of the final CRF will remain at the investigator's site at the completion of the study.

The CRF numbering convention is as follows:

01 - 2 - 3 - 4 - A -B -A

01: Site # must be 2 digits (use leading zero) --- (sites 01-05)

2 - 3 - 4: patient screening/enrollment # (001 – 065)—must be 3 digits

A-B-A: Patient initials (if no middle initial, use dash)

Total 5 digits and initials for enrolled patients.

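### The screen-failure rule in section 9 catches every run-in patient treated as section 9.1 plans, yet those patients count toward the 65; ignoring the rule pools unguided patients into the efficacy estimates

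*Combined protocol and SAP*

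**What the plan says.** All references are to the combined protocol and SAP.

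- **Section 9.1, run-in.** In a first cohort of up to 15 patients, CMA mapping "will be performed but will not be utilized to guide the ablation procedure". The section adds: "That is, ablation will be based on standard approaches only". The run-in may be cut below 15 if the software converges consistently within five minutes.
- **Section 9.1, guided patients.** "In the second cohort of patients (potentially patients 16-65", in the protocol's numbering), the map is used to point the operator to regions to interrogate and, if the activity persists, ablate.
- **Section 9, screen failure.** A patient is a screen failure "if a patient does not have any ablation performed that is a result of the mapping completed by the CMA software". No cohort is excepted. The section continues: "Patients who are deemed to be screen failures may be considered for re-enrollment should they require a later AF ablation procedure".
- **Section 10.4.1.** During follow-up, "patients will be allowed a second ablation procedure using the CMA software should recurrence of AF occur".
- **Protocol Summary.** The first primary endpoint, the acute procedural outcome, is attached to procedures on all 65 patients. Section 6.1 lists freedom from AF at 12 months after one and after two procedures as the other primary endpoints.
- **Section 13.1.** The CRF has one "patient screening/enrollment" number series, 001 to 065.
- **Section 17.** Descriptive statistics are planned; no analysis set is named.

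**The concern.** The same patients are planned as part of the 65 and excluded by a rule that has no exception for them. Ablation by standard approaches alone is not a consequence of the CMA map, even where a lesion happens to fall on a site that the map marked. A run-in patient treated exactly as section 9.1 directs therefore meets the screen-failure definition at the index procedure.

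Three things depend on how this is resolved:

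- **Who is in the efficacy estimates.** Section 8 says the sample is meant to give preliminary estimates of safety and performance. An estimate for map-guided ablation should not include patients whose ablation was unguided by design, and nothing in the plan keeps them out.
- **What counts as the second procedure.** If a run-in patient has AF again and undergoes a CMA-guided ablation, section 10.4.1 makes that the second procedure. Section 9 would allow it to be a new index procedure under a new enrollment. Two primary endpoints depend on the count of procedures.
- **Who is in the safety denominator.** Run-in patients undergo the investigational mapping, for which section 12 lists longer procedure time and added anesthesia.

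The study is unblinded, so leaving this open allows set membership to be decided after outcomes are known.

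**Working it through.** **1. Reproduce the plan's count.** Patients 16 to 65 inclusive: 65 − 16 + 1 = 50. Run-in 15 + guided 50 = 65, which matches section 8. The run-in is inside the 65, not in addition to it.

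**2. Apply the section 9 rule literally.** With a run-in of k patients, the share caught is k/65 and 65 − k remain.

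| k | Share of 65 | Remaining |
|---|---|---|
| 15 | 15/65 = 23.1% | 50 |
| 10 | 10/65 = 15.4% | 55 |
| 5 | 5/65 = 7.7% | 60 |

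**3. Ignore the rule and pool.** Let g be the success rate in guided patients and u the rate in run-in patients. With k = 15:

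pooled rate = (50g + 15u)/65 = g − (15/65)(g − u)

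The pooled rate therefore differs from the guided rate by 0.231 × (g − u). The documents give no value for g − u, so the gaps below are assumptions:

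- 10 points: 2.3 points
- 20 points: 4.6 points
- 30 points: 6.9 points

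If u is below g, pooling understates the guided rate; if u is above g, it overstates it.

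**4. Safety, if run-in patients were dropped.** For an event type not observed at all, the exact two-sided 95% upper bound is 1 − 0.025^(1/n):

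- n = 65: 5.5%
- n = 50: 7.1%

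**5. Precision with guided patients only.** Exact (Clopper-Pearson) 95% intervals at an assumed 60% success rate:

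- 39/65: 47.1% to 72.0%, half-width 12.4 points
- 30/50: 45.2% to 73.6%, half-width 14.2 points

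The difference is 14.2 − 12.4 = 1.8 points. The set is 50 whether the literal rule removes the run-in patients or the analysis is restricted to guided patients on purpose. This figure is therefore a cost of the remedy and does not measure harm from the defect.

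**The case against.** The strongest reply is that the specific rule governs the general one. Section 9.1 sits within section 9, deals expressly with these patients, describes them as a validation cohort and numbers them among the 65. On that reading the screen-failure sentence was meant for guided patients and merely lacks an exemption. That is probably the intent. It does not settle the matter: once the rule is set aside, nothing separates unguided from guided patients, and the Protocol Summary points to pooling them. A figure is also missing from section 9, and what it shows is unknown; the readable text conflicts without it.

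Several stronger readings are tempting, and the documents do not support them:

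- **Run-in patients lose follow-up and drop out of safety reporting.** Section 9 says patients are enrolled at consent and followed for 12 months, and section 11 requires an adverse-event tally for study patients whatever the cause. Nothing says treated patients leave it. The remaining gap is that the status of treated screen failures is not stated.
- **Patients will be counted twice.** Re-enrollment is only permitted, so double counting is a possibility and not a plan.
- **The rule excludes run-in patients for good.** It is not tied to the index procedure, so a later CMA-guided ablation might be argued to lift it. The claim holds at the index procedure.
- **Section 10.3 orders guided ablation in the run-in.** Its driver step, "All drivers are to be sequentially ablated or isolated using the St Jude Ensite system", has no cohort label, but section 9.1 is specific and should govern. This is a labelling gap.
- **The study's decision rule is damaged.** Section 8 sets the size on feasibility grounds, and the plan has no hypothesis test or success threshold. What is at risk is the meaning of the estimates.

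**Conclusion.** The point holds as a conflict in the wording, with a direct consequence for the analysis sets. Up to 15 of 65 patients (23%) are planned, treated and numbered as study patients while meeting the screen-failure definition at their index procedure. Taken literally, the plan removes them and lets them re-enroll. Taken as probably intended, it mixes them into the efficacy estimates, moving the pooled rate 2.3 to 6.9 points from the guided rate for assumed gaps of 10 to 30 points.

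The share affected rests on the plan's own numbers and on a full run-in of 15; it falls if the run-in is shortened. The size of the pooling shift rests wholly on the assumed gap. The change in the zero-event safety bound, from 5.5% to 7.1%, applies only if treated run-in patients were dropped from the safety set, which the documents do not say will happen.

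This should be corrected before the analysis.

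**What to change.** 1. In section 9, limit the screen-failure rule on map-driven ablation to guided patients.
2. State that run-in patients treated under section 9.1 remain enrolled with 12-month follow-up, and that a later CMA procedure in them is a second procedure under section 10.4.1, not a re-enrollment.
3. In section 17, report run-in and guided patients separately. Use guided patients (about 50) for the acute and 12-month efficacy estimates, and all mapped and treated patients for safety. Amend the Protocol Summary, since this changes the denominator it attaches to the acute primary endpoint.
4. Add a run-in/guided field to the CRF. Avoid the labels first and second cohort, which section 8 already uses for AF duration.

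Cohort labels on the driver steps in section 10.3 would help but are optional. Whether the ban on empiric ablation covers run-in patients is for the sponsor to decide: section 9.1 gives them standard approaches, section 3 lists empiric CFAE and linear lesions among standard-of-care techniques, and section 10.3 states the ban without a cohort label.

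The cost is protocol wording and one CRF field, with no added patients or visits. The efficacy set becomes about 50 instead of 65, or about 1.8 points more exact interval half-width at an assumed 60% rate. Run-in patients with recurrence can no longer re-enter as new guided patients.

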Extensive retrospective evaluation of CMA has been performed and published^{3,4}. A total of 70 patients have been mapped using CMA at Mercy Hospital in St. Louis, MO, University of Kansas Medical Center in Kansas City, KS, and Mount Sinai Hospital in New York, NY. No adverse events were associated with the mapping process. Fifty-five of the 70 mapped patients produced analysis that was usable. The unusable patient data can be attributed to initial tuning of the signal processing algorithms. In this 55 patient series of data, patients were mapped using CMA and subsequently ablated with standard of care ablation at the operator’s discretion, without the benefit of the CMA generated maps. Ablation techniques included Wide Area Circumferential Ablation (WACA), empiric Complex Fractionated Atrial Electrogram (CFAE) Ablation and empiric linear lesion Ablation. Retrospectively, the data was analyzed to see the effects of incidental ablation of CMA identified AF Driver domains. Ultimately, the use of CMA generated maps of AF driver domains may serve to reduce the amount of empiric CFAE and linear lesion ablation and improve outcomes in persistent AF patients.

The Abstract and Conclusion sections from the journal article entitled “***Characterization of Drivers in Patients with Persistent Atrial Fibrillation to Identify Substrate Based Rotor Ablation Targets***” serve as a good overview of CMA and associated retrospective clinical findings:

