ABSTRACT: Recent clinical trials have shown that targeting rotors and focal impulses (FIs) during atrial fibrillation (AF) ablation improves outcomes. This study evaluated whether a novel computational mapping algorithm (CMA) could identify FIs and rotors, and characterize rotors when incidental ablation resulted in rhythm changes. Three-dimensional (3D) left atrial electroanatomic maps were created from signals recorded from multipolar circular mapping catheters in 61 patients undergoing persistent AF ablation. Forty of 61 acquired patient datasets were of adequate quality for analysis CMA, employing an AF pattern recognition algorithm, creating 3D panoramic AF maps identifying drivers of AF (FI and rotors) post procedure. Rotors were further classified as substrate (SBR) or non-substrate based (NSBR) on the basis of rotor stability, proximity to voltage transition zones and complex fractionated atrial electrograms (CFAEs). Incidentally ablated identified AF drivers, including SBRs and NSBRs, were evaluated for rhythm changes. A total of 172 drivers were identified in 40 patients (4.3 ± 2.2 drivers/patient). Seventy percent were rotors (120/172) and 30% were FIs (52/172). Sixty-seven percent of rotors were classified as SBR vs 33% as NSBR. Incidental ablation of SBRs resulted in rhythm change 91% of the time versus only 24% of the time for NSBR ($p < 0.0001$).

CONCLUSIONS: Incidental ablation of SBRs resulted in rhythm change significantly more frequently than ablation of NSBRs. Identification of drivers and classification of rotors based on substrate properties may allow a more tailored ablation approach in patients with persistent AF.

The following is a description of what each Mapping System will perform during Persistent Atrial Fibrillation cases:

St. Jude Ensite System:

1. Tracking the position of the catheters as they travel through the heart and displaying them on a screen in 3D so that X-Ray is not needed (or reduced).
2. Create a shell of the heart chamber and display on a screen so that the physician knows where the catheters are in relation to the anatomy (shell of heart chamber).
3. Display electrogram signals from all the electrodes on the different catheters in the heart.

These three features will be used for the entire case to determine where to ablate tissue.

AFTx System:

1. Receive the heart chamber shell from St Jude Ensite.
2. Receive the electrogram signals from St Jude Ensite.

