8 SAMPLE SIZE

This safety and efficacy study will enroll 65 patients across 1-5 US centers and 1-2 OUS centers. This number has been determined on the basis of study feasibility and not by statistical means. This is a feasibility study of the mapping system performance in which the sample size of the clinical investigation is intended to provide preliminary estimates of safety and performance.

The study will involve two cohorts. The first cohort will be composed of patients with persistent AF > 7 days but < 1 year's duration. The second cohort will be composed of up to 15 patients with long-standing persistent AF (AF > 1 year's duration).

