- Phrenic nerve damage: damage to the nerve that controls the diaphragm and may affect your breathing. Symptoms may be temporary but in some cases can be permanent (respiratory arrest) (<1%).
- Pneumonia: infection of lungs or gathering of fluid in the lungs (<1%).
- Pseudoaneurysm: development of a false pouch in the vessel wall. This can be caused by movement of catheters in the blood vessels. This may heal on its own, but sometimes need surgical repair (<1%).
- Radiation injury resulting in dermatitis (skin burns): (<1%).
- Respiratory failure: damage to breathing that can be permanent (respiratory arrest) (<1%).
- Radiation exposure during the fluoroscopic imaging of the catheters during ablation: this may slightly increase the lifetime risk of developing a fatal malignancy or a genetic defect in offspring (<1%).
- Fluid overload: excessive fluid built up could result in pulmonary (lung) edema; congestive heart failure (CHF) may occur or may be exacerbated (worsened) due to delivery of sterile salt water (saline) during the procedure (these risks are specific to open irrigated ablation catheters) (1.5%).

Potential Risks Associated with investigational mapping system:

- The additional investigational mapping done for this study may cause patients to have a prolonged procedure time. The patients may be exposed to additional anesthesia as a

- result of this prolonged procedure time.
- Potential harms of a more extensive bi-atrial lesion set over PV isolation include prolonged procedure time and atrial stunning.

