17 DATA ANALYSIS

This clinical study is a proof of concept study intended to assess the feasibility of the study mapping system. Baseline clinical characteristics (e.g. age, gender, renal function) and procedural characteristics (e.g. surface intracardiac electrogram and imaging findings) of the patients will be collected and analyzed.

Descriptive statistical data will be used to draw up the characteristics of subjects at the time of enrollment (demographics, baseline data). Quantitative parameters will be described using the following summary descriptive statistics: mean, standard deviation, median, and minimum and maximum values. Qualitative parameters will be described overall using frequencies and percentages. Percentages will be calculated on the number of non-missing observations. In all cases, the number of missing values will be specified.

Wilcoxon's test or Student's test for pairwise comparisons will be used, depending on the normality of the distribution, to study evolution in time.

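### Section 17 reports safety as percentages without limits, so zero events would read as 0%, although 0/15 leaves rates up to 18.1% open and 0/65 up to 4.5%

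*Combined protocol and SAP*

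**What the plan says.** Section 8 sets the size at 65 patients on feasibility grounds and says that the "sample size of the clinical investigation is intended to provide preliminary estimates of safety and performance". Section 6.1 lists procedure-related adverse events, major adverse cardiac events and serious adverse events among the additional endpoints.

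Section 17 has no separate rule for these endpoints. The only one that can apply is the general rule for categorical data: "Qualitative parameters will be described overall using frequencies and percentages". It mentions no confidence interval or limit and no breakdown by cohort.

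Section 9.1 describes a run-in cohort of up to 15 patients who are mapped but whose maps do not guide ablation. It supports this cohort with earlier experience of mapping alone, in which the cited investigators "have seen no procedure related adverse events in over 61 patients. As such, it is safe and worthwhile". The conclusion in full is that "it is safe and worthwhile to take an initial cohort of patients to normalize the mapping process".

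Section 3 gives a larger count, 70 mapped patients, and states: "No adverse events were associated with the mapping process". It describes the timing in two ways. Its account of the 55 usable cases has patients mapped and then ablated without the maps. The abstract that it reproduces, on 61 patients, describes "creating 3D panoramic AF maps identifying drivers of AF (FI and rotors) post procedure".

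Section 12 names a risk of the mapping itself, without a rate: "The additional investigational mapping done for this study may cause patients to have a prolonged procedure time". It adds that this may mean more anesthesia.

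**The concern.** A point estimate of 0% from a small sample says little about how large the true rate could be. Where a study exists partly to estimate safety, the upper limit carries the information, and section 17 does not ask for it. Readers of the final report would see 0%, or a low percentage, and would have to work out the precision themselves.

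Section 9.1 shows how such a count can be used. It goes straight from no observed events to a statement that the run-in is safe, with no limit in between. The earlier count also has two denominators and an unclear relation to the exposure in this trial.

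What is at stake is what the trial can later be said to have shown about safety. No test, decision rule or sample size depends on it.

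**Working it through.** **Inputs**
- Prior count: 0 in over 61 (section 9.1), taken as 61; 0 in 70 (section 3).
- This trial: up to 15 run-in patients (section 9.1); 65 patients in total (section 8), taking all 65 as mapped.
- Harm rate: none is given for mapping. The figure of 2% is an assumption, of the same size as some ablation risks in section 12. Rates of 1% and 3% show the range.

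The plan gives raw counts only, so there is no calculated figure of its own to reproduce. The 61 in section 9.1 agrees with the number in the abstract in section 3.

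**Upper limit for zero events (exact, Clopper-Pearson)**

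One-sided 95%: 1 − 0.05^(1/n). Upper end of the two-sided 95% interval: 1 − 0.025^(1/n).

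| Count | One-sided | Two-sided |
|---|---|---|
| 0/15 | 18.1% | 21.8% |
| 0/61 | 4.8% | 5.9% |
| 0/65 | 4.5% | 5.5% |
| 0/70 | 4.2% | 5.1% |

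For example, 1 − 0.05^(1/61) = 0.0479. A run-in shortened below 15, which section 9.1 allows, gives a limit above 18.1%.

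**Chance of seeing no event at true rate p: (1 − p)^n**
- n = 61: 0.99^61 = 54%; 0.98^61 = 29%; 0.97^61 = 16%.
- n = 70: 0.98^70 = 24%.
- n = 65: 0.98^65 = 27%.
- n = 15: 0.98^15 = 74%.

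**Size needed to bring the limit to 2% or less with zero events**

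One-sided: ln(0.05)/ln(0.98), rounded up, is 149 patients. Two-sided: ln(0.025)/ln(0.98), rounded up, is 183. Neither the earlier series nor this trial is that large.

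**What the prior count covers**
- Catheter sampling: covered. The abstract says that signals were recorded with circular catheters in patients undergoing ablation.
- Computation during the case: possibly not covered, because the abstract places map creation after the procedure. The other account in section 3 has mapping before ablation.
- Ablation guided by the maps: not covered. Section 3 says that operators ablated without them. Patients from about the 16th onward will have it.

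**The case against.** The strongest reply is that section 9.1 is background. It justifies a small run-in in which patients receive standard ablation, and nothing in the design depends on the sentence. Sections 8 and 17 present a feasibility and proof-of-concept study, and no section says that a zero count will be read as proof of safety. The mapping risk is disclosed in section 12, adverse events are recorded from the procedure onward, and the Data Monitoring Committee reviews safety every 6 months. All of this stands, and it makes the point one of reporting rather than conduct. It does not supply the missing limit. An exact limit needs no hypothesis or power, and an estimate without its precision serves the aim in section 8 poorly.

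Three stronger readings are tempting, and the documents do not support them.

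- A reader might infer that section 9.1 declares the mapping system safe. The full sentence is limited to taking an initial cohort.
- A reader might infer that sampling during the case was never tested because the maps were made afterwards. The abstract shows that the signals were collected in patients undergoing ablation. Only computation time is in doubt, and section 9.1 refers to convergence within five minutes.
- A reader might infer that zero procedure-related events is implausible beside the ablation risks in section 12. The five rates of 1.5% or 2% (vascular access, thrombus, AV fistula, hematoma, fluid overload) sum to 8.5%, and 0.915^61 = 0.4%. That sum requires the categories not to overlap. If the broad vascular-access item contains the next three, the total is 2% + 1.5% = 3.5%, and 0.965^61 = 11%. Section 9.1 also limits its statement to mapping alone, which agrees with section 3.

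**Conclusion.** The point holds as a gap in reporting. With no events, section 17 as written would report 0%, while the data would leave one-sided 95% upper limits of 18.1% for a full run-in cohort and 4.5% for 65 mapped patients. Section 9.1 already relies on a zero count in this way. Its evidence is compatible with rates up to 4.8% (0/61) or 4.2% (0/70) one-sided, so the conclusion does not depend on which count is right.

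Three assumptions matter. The 2% rate is a benchmark chosen for illustration. The 0/65 limit takes all 65 patients as mapped. That the 61 in section 9.1 is the series in the abstract is inferred from the matching number and author group.

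The documents do not show that mapping is harmful. They show that the counts cannot exclude rates of a few percent, and that the plan has no place to say so.

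**What to change.** **Section 17.** Report each safety endpoint as a count, a percentage and an exact binomial upper limit (one-sided 95%, or the two-sided interval, chosen in advance). Do this for the run-in cohort of section 9.1 and for all mapped patients. State that a zero or low count will not be described as showing safety beyond that limit.

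Define all mapped patients explicitly. Section 9 classes a patient as a screen failure if no ablation results from the map. Those patients have had the mapping and belong in the safety denominator. Read literally, that rule would also remove the whole run-in cohort, whose maps are not used to guide ablation.

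**Section 9.1.** Give the prior count with its upper limit: 4.8% for 0/61 or 4.2% for 0/70, one-sided. Reconcile the figure of over 61 with the 70 in section 3, and reconcile the two descriptions in section 3 of when the maps were made. Say that the prior data do not cover map-guided ablation and may not cover computation time during the case.

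**Cost.** Wording in two sections and a few exact limits on counts that will be collected anyway. The downside is a less favourable safety statement, with an upper limit of about 4% to 5% from the prior data in place of the word safe.
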